4.4.3.3 Mini Mental State Examination

Mini mental state examination (MMSE) consists of 11 types of questions/activity. In each type, the number of questions can range from 1 to 5. Score one point for each correct response for each question or activity within each type.

According to MMSE manual, the total score will be calculated by summing the item scores across all 11 types of questions/activities. The possible maximum total score is 30.

4.4.3.4 The University of Miami Parkinson's Disease Hallucinations Questionnaire

The University of Miami Parkinson's Disease Hallucinations Questionnaire (UM-PDHQ) consists of 6 quantitative questions (Q1 to Q6) regarding severity of hallucinations and 14 qualitative questions regarding quality of hallucination (Q7 to Q20). Question 1 is a gating question to assess the presence or absence of hallucination.

The scoring ranges are not uniform in each item (Q3 and Q4: 0-2; Q2:0-4; Q5: 1-3; and Q6:0-3). According to the information on the questionnaire (total score [min=0, max=14]), the total score from 6 quantitative questions will be calculated by summing the response scores over Q2 to Q6

if the answer of Question 1 is 1 or 2 while total score is equal to zero if the answer for Question 1 is zero (i.e. no hallucinations).

4.4.3.5 Parkinson's disease Fatigue Scale

Parkinson's disease fatigue scale (PFS-16) consists of 16 questions. According to Appendix 15 of protocol, the responses to each question are "Strongly disagree", "Disagree", "Neither agree nor disagree", "Agree", and "Strongly agree". The scoring method used for the study is

PFS-16 Response	Score
Strongly disagree	1
Disagree	2
Neither agree nor disagree	3
Agree	4
Strongly agree	5

The total score will be calculated by summing scores over 16 questions. [2, 3] The possible total scores range from 16 to 80.

4.4.3.6 Patient Assessment of Constipation Symptoms

Patient Assessment of Constipation Symptoms (PAC-SYM) is about constipation in the past two weeks and consists of 12 items. The scores for each item is

PAC-SYM Response	Score
Absent	0
Mild	1
Moderate	2
Severe	3
Very Severe	4

There are total score and 3 subdomain scores: abdominal symptoms (Item 1-4), rectal symptoms (Item 5-7), and Stool symptoms (Item 8-12). Following the information booklet (2nd Edition, May 2015) from Mapi Research Trust, a subscale score is calculated as the average item score of non-missing items within that subscale. Total score is the average score of non-missing items within the instrument.

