APPENDIX 16: PATIENT ASSESSMENT OF CONSTIPATION SYMPTOMS

PAC-SYM

This questionnaire asks you about your constipation in the past 2 weeks. Answer each question according to your symptoms, as accurately as possible. There are no right or wrong answers.

For each symptom below, please indicate how severe your symptoms have been during the past 2 weeks. If you have not had the symptom during the past 2 weeks, check 0. If the symptom seemed mild, check 1. If the symptom seemed moderate, check 2. If the symptom seemed severe, check 3. If the symptom seemed very severe, check 4. Please be sure to answer every question.

How severe have each of these symptoms been in the last 2 weeks	Absent	Mild	Moderate	Severe	Very Severe
	0	1	2	3	4
Discomfort in your abdomen					
Pain in your abdomen					
Bloating in your abdomen					
Stomach cramps					
Painful bowel movements					
Rectal burning during or after a bowel movement					
Incomplete bowel movement, like you didn't "finish"					
Bowel movements that were too hard					
Bowel movements that were too small					
Straining or squeezing to try to pass bowel movements					
Feeling like you have to pass a bowel movement but you couldn't (false alarm)					

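### The SAP's 12-item PAC-SYM key and its PAC-QOL label table do not fit the forms printed in the protocol, so item membership and coding need to be reconciled before scoring

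*SAP*

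**What the plan says.** **PAC-SYM.** SAP 4.4.3.6 states that the instrument "is about constipation in the past two weeks and consists of 12 items". It defines three subscales by item number: "abdominal symptoms (Item 1-4"), then "rectal symptoms (Item 5-7), and Stool symptoms (Item 8-12"). The scoring source is external: "Following the information booklet (2nd Edition, May 2015) from Mapi Research Trust". Missing answers are handled by averaging: "a subscale score is calculated as the average item score of non-missing items within that subscale". No minimum number of answered items is given.

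Protocol Appendix 16 prints the questionnaire as a table without item numbers. As supplied, it has four abdominal rows, then painful bowel movements, "Rectal burning during or after a bowel movement", "Incomplete bowel movement", too hard, too small, straining, and false alarm.

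**PAC-QOL.** SAP 4.4.3.7 gives one 0-4 table with paired labels. One member of each pair runs *Never, Rarely, Sometimes, Often, Always*. The other runs from *Not at all* to *Extremely*, with *A lot* at score 3. The same section then reverses items 18 and 25 to 28, using different labels: *Quite a bit*, and a scale from *None of the time* to *All of the time*. Appendix 17 prints the labels of the reversal list. Its printed codes run 1-5 for items 1-6, 13-18 and 22-24, and 0-4 for the others.

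SAP 4.4.3 calls questionnaire data exploratory. SAP 7.7.1 nevertheless reports the PAC-SYM total with three subscales and the PAC-QOL total with four.

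**The concern.** A key that assigns items by number works only if the form has the same items in the same order. Eleven rows cannot fill twelve positions. The averaging rule would not show the gap, because an item that was never asked is treated like one left blank. The subscale still gets a value under its usual name.

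For PAC-QOL, the forward table does not give a score for every response a patient could tick. A programmer has to infer the mapping, and the numbers printed on the form are the obvious thing to fall back on. They are on two different scales.

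At stake are the levels, and in some cases the changes from baseline, of the two constipation questionnaires. Adding scoring detail for each questionnaire is the first purpose given for the SAP amendment (SAP section 1), so this is the place where the mapping should be settled.

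**Working it through.** **1. PAC-SYM count.** The SAP ranges give 4 + 3 + 5 = 12 items, which agrees with the SAP's own figure. Appendix 16 as supplied gives 11 rows.

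**2. Mapping by row position.** Assume the printed form was used, rows are numbered from the top, and the order follows the key.

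| SAP range | Rows it picks up |
|---|---|
| Abdominal 1-4 | discomfort, pain, bloating, cramps |
| Rectal 5-7 | painful movements, rectal burning, incomplete movement |
| Stool 8-12 | too hard, too small, straining, false alarm, no twelfth row |

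The four abdominal rows fill their range. Seven rows remain for 3 + 5 = 8 positions, so one position is empty. The documents do not say which. The possibilities are:

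- **A: the absent item is rectal.** Row 7 then belongs with the stool items. Scoring by position changes both subscales. Write a, b, c for rows 5, 6, 7 and s for the sum of rows 8-11.
  - Rectal: (a+b+c)/3 − (a+b)/2 = c/3 − (a+b)/6, which ranges from −1.33 to +1.33.
  - Stool: s/4 − (s+c)/5 = s/20 − c/5, which ranges from −0.80 to +0.80.
- **B: the absent item is a stool item.** The rectal range is then right, and stool rests on 4 of its 5 items.
- **C: the form in use has all 12 items in the key's order.** The SAP ranges then stand, and only Appendix 16 is wrong.

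The abdominal score is the same in A, B and C. Reassigning the 11 rows between subscales does not change their overall mean, but in A and B that mean is an 11-item total.

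**3. PAC-QOL labels.** Items 18 and 25-28 are reversed, so 28 − 5 = 23 are scored forward. Twelve of these (3-6, 13-17, 22-24) use the time scale, and none of its five printed responses is in the forward table. Eleven (1-2, 7-12, 19-21) use the extent scale, and *Quite a bit* is not in the table. All 23 therefore have at least one response with no stated score.

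**4. PAC-QOL codes.** Items printed 1-5: 6 + 6 + 3 = 15. Items printed 0-4: 6 + 3 + 4 = 13. If printed codes were stored unrecoded, each forward item printed 1-5 would be 1 too high. The subscale offset is the number of such items divided by the number of items. Item 18 is left out because the SAP scores it by its reversal labels.

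| Score | Items | Forward items printed 1-5 | Offset |
|---|---|---|---|
| Physical discomfort | 4 | 4 | 4/4 = 1.00 |
| Psychosocial | 8 | 2 | 2/8 = 0.25 |
| Worries | 11 | 7 | 7/11 = 0.64 |
| Satisfaction | 5 | 1 | 1/5 = 0.20 |
| Total | 28 | 14 | 14/28 = 0.50 |

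**5. Change from baseline.** The offset cancels when the same items are answered at both visits. In physical discomfort it is 1.00 whichever items are missing, so it always cancels. In a mixed subscale it can fail to cancel. With all eight psychosocial items at baseline the offset is 2/8 = 0.25. With items 5 and 6 missing later it is 0/6 = 0, so the change is off by −0.25. Two of eight missing is within the SAP's 50% limit.

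**The case against.** The strongest reply is that neither mismatch proves a scoring error.

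- **The key is external.** The PAC-SYM ranges come from the scoring booklet, and the rows in Appendix 16 carry no numbers. SAP 8.3 says questionnaire parameters follow the instruments' manuals, with special rules in the ADaM specifications. If the eCRF holds 12 items in the booklet's order, nothing needs rescoring. This stands, and it is why the point is conditional.
- **A row may have been lost.** Appendix 16 is a table read from PDF, and neighbouring Appendix 17 has visibly lost some header numbers. This cannot be excluded. It is settled by looking at the form.
- **The 2017 appendix may not be the form used.** SAP 2.1 says that, apart from the dose range and the removal of randomization, nothing changed from the 27 July 2017 protocol. Yet the SAP scores BDI-II, while Appendix 10 is titled BDI and has no a/b options for items 16 and 18. Forms may therefore differ from the appendices.
- **PAC-QOL is scored by label.** If every response is mapped by label to 0-4, there is no offset. That is correct, but the forward table does not contain the labels needed.
- **Item-level data are listed** (SAP 7.9), so an error could be found and rescored. This limits the harm but does not replace a stated rule.

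A reader might infer that the subscales are certainly mis-built, that incomplete evacuation will be reported as a rectal symptom, or that rectal should be rows 5-6 and stool rows 7-11. The documents do not support this, because they show neither which item is absent nor where incomplete evacuation belongs. A reader might also infer a worries offset of 8/11 = 0.73. That counts item 18, which the SAP reverses by label. Nor do the offsets cancel only when no item is missing; step 5 shows the actual condition.

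**Conclusion.** The scoring rules in SAP 4.4.3.6 and 4.4.3.7 cannot be applied as written to the forms printed in the protocol.

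For PAC-SYM, if the 11-row form was used, at least one of the rectal and stool subscales is wrong or short. Under assumption A the difference is at most 1.33 points (rectal) and 0.80 points (stool) on the 0-4 scale. If a 12-item form in the key's order was used, there is no scoring error, and the appendix alone needs correcting.

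For PAC-QOL, the mismatch of labels and codes is visible in the documents. The offsets of 1.00, 0.25, 0.64 and 0.20 are conditional on unrecoded storage, which would itself depart from the SAP's 0-4 scoring. They would mainly affect levels, and changes only where the answered items differ between visits in a mixed subscale.

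These are exploratory scores, summarised descriptively. The primary CSBM success endpoint comes from the stool diary, and neither it nor the sample size is touched.

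**What to change.** 1. Compare Appendix 16 and the eCRF with the 12-item scoring key, and correct whichever is wrong.
2. In SAP 4.4.3.6, list the items of each PAC-SYM subscale by wording rather than number. If an item was not collected, say so and label the affected subscale and the total as modified.
3. In SAP 4.4.3.7, replace the forward table with the form's own response labels, consistent with the reversal list. State that the 15 items printed 1-5 are recoded to 0-4 before any reversal or averaging.

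The cost is a check of the forms, a few lines of SAP text and a coding map. No new data are needed. An item that was never asked cannot be recovered, which is why it has to be declared.

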4.4.3.7 Patient Assessment of Constipation Quality of Life

Patient Assessment of Constipation Quality of Life (PAC-QoL) is to measure the impact constipation has had on subject's daily life over the past 2 weeks.

PAC-QoL: 2 Sets of Responses separated by “/” Depending on questions	Score
Not at all / Never	0
A little bit / Rarely	1
Moderately / Sometimes	2
A lot / Often	3
Extremely / Always	4

PCAC-QoL contains 28 items grouped into 4 subscales: Physical discomfort (Item 1-4), Psychosocial discomfort (Item 5-12), Worries and concerns (Item 13-23), and satisfaction (Item 24-28).

Following the information booklet (4th Edition, May 2015) from Mapi Research Trust, scores of items 18 and 25 to 28 are reversed meaning that the score corresponding to the response:

- “Not at all”/”None of the time” will be 4
- “A little bit”/”A little of the time” will be 3
- “Moderately”/”Some of the time” will be 2
- “Quite a bit”/”Most of the time” will be 1
- “Extremely”/”All of the time” will be 0

Then, subscale score are calculated as the average item scores of non-missing items within that subscale. Total score is calculated as the mean of 28 item score within the instrument. When more than 50% of items are missing for a subscale score, then that subscale score is set to missing. If a subscale is missing, the PAC-QoL total score is set to missing.

4.4.3.8 REM Sleep Behavior Disorder Screening Questionnaire

REM sleep behavior disorder screening questionnaire (RBDQ) comprises 10 items. Each item is answered as yes/no (yes=1 or no =0). According to Scaling and Scoring (Version 1.0: Sept 2016) from Mapi Research Trust, total score will be summed over all items/questions. The maximum score is 13 points. A score of 0 is given to item/question is not answered. The multiple answers for an item will be considered as missing data.

4.4.3.9 Unified Parkinson's disease Rating Scale

Unified Parkinson's disease rating scale (UPDRS) consists of

- Part I: Non-Motor Aspects of Experiences of Daily Living (nM-EDL) - Q1.1 to Q1.6 completed by rater; Q1.7 to Q1.13 completed by subject
- Part II: Motor Aspects of Experiences of Daily Living (M-EDL) - Q2.1 to Q2.13 completed by subject
- Part III: Motor Examination - Q3.1 to Q3.18 completed by examiner
- Part IV: Motor Complications - Q4.1 to Q4.6 by rater

Rating for items is from 0 (normal) to 4 (severe). Score for each part is obtained from the sum of corresponding item scores. Total score is the summed score from the scores of 4 parts,

4.4.3.10 Other Questionnaires

Trail make A& B and Parkinson's disease Sleep Scale (PDSS) will not be used for analyses but will be listed only.

ROME-IV Criteria for Constipation (ROME-IV) is only collected at screening. It will be listed.

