Exploratory analyses will also be done with respect to the sleep data, the body temperature data, mood, fatigue, hallucinations, overall NMS scale and all other questionnaires and neurocognitive tests. These parameters will be summarized numerically and graphically. There will also be comparisons done of changes over time within a patient (i.e. between baseline, end run-in period, and at the end of the fixed dose period, Period 3.2) and differences between groups (i.e. between patients in the Enterin arm and in the placebo arm at the end of period 4). As before, continuous measurements within a patient will be compared with a paired t-test (transforming the data if necessary) and continuous measurements between patient groups will be compared with a two-group t-test (transforming the data if necessary). In addition, these data will be analyzed using a mixed linear model since there are multiple measurements over time. Categorical data will be

compared with a chi-squared test or a Fisher's exact test if the expected cell counts are too small

for a chi-squared test.

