APPENDIX 9: NON-MOTOR SYMPTOMS QUESTIONNAIRE (NMSQ)

Have you experienced any of the following in the last month?

		Yes	No			Yes	No
1	Dribbling of saliva during the daytime.			16	Feeling sad, 'low' or 'blue'.		
2	Loss or change in your ability to taste or smell.			17	Feeling anxious, frightened or panicky.		
	Difficulty swallowing food or drink or problems with choking.			18	Feeling less interested in sex or more interested in sex.		
4	Vomiting or feelings of sickness (nausea).			19	Finding it difficult to have sex when you try.		
5	Constipation (less than three bowel movements a week) or having to strain to pass a stool.	s 		20	Feeling light-headed, dizzy or weak standing from sitting or lying.		
6	Bowel (faecal) incontinence.			21	Falling.		
7	Feeling that your bowel emptying is incomplete after having been to the toilet.			22	Finding it difficult to stay awake during activities such as working, driving or eating.	s 	
8	A sense of urgency to pass urine makes you rush to the toilet.			23	Difficulty getting to sleep at night or staying asleep at night.		
9	Getting up regularly at night to pass urine.			24	Intense, vivid or frightening dreams.		
10	Unexplained pains (not due to known conditions such as arthritis).			25	Talking or moving about in your sleep, as if you are 'acting out' a dream.		
11	Unexplained change in weight (not due to change in diet).			26	Unpleasant sensations in your legs at night or while resting, and a feeling that you need	_	_
12	Problems remembering things that have happened recently or forgetting to do things.			27	to move. Swelling of the legs.		
13	Loss of interest in what is happening around you or in doing things.				Excessive sweating. Double vision.		
14	Seeing or hearing things that you know or are told are not there.			30	Believing things are happening to you that other people say are not.		
15	Difficulty concentrating or staying focussed.						

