APPENDIX 18: REM SLEEP BEHAVIOR DISORDER SCREENING QUESTIONNAIRE

- 1. I sometimes have very vivid dreams. yes/no
- 2. My dreams frequently have an aggressive or action-packed content. yes/no
- 3. The dream contents mostly match my nocturnal behavior. yes/no
- 4. I know that my arms or legs move when I sleep, yes/no
- 5. It thereby happened that I (almost) hurt my bed partner or myself. yes/no
- 6. I have or had the following phenomena during my dreams:
 - 6.1. Speaking, shouting, swearing, laughing loudly yes/no
 - 6.2. Sudden limb movements, "fights" yes/no
 - 6.3. Gestures, complex movements, that are useless during sleep, e.g., to wave, to salute, to frighten mosquitoes, fall off the bed yes/no
 - 6.4. Things that fell down around the bed, e.g., bedside lamp, book, glasses yes/no
- 7. It happens that my movements awake me. Yes/no
- 8. After awakening I mostly remember the content of my dreams well. Yes/no
- 9. My sleep is frequently disturbed. Yes/no
- 10. I have/had a disease of the nervous system (e.g., stroke, head trauma, Parkinsonism, RLS, narcolepsy, depression, epilepsy, inflammatory disease of the brain), which? yes/no

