APPENDIX 19: PARKINSON'S DISEASE SLEEP SCALE

your expe	d you rate the following, based on rience during the past one week. s at the appropriate point on the line)	and the second	
The overall quality of your night's sleep is:	AWFUL	EXCELLENT	0 1 2 3 4 5 6 7 8 9 10
. Do you have difficulty falling asleep each night?	ALWAYS	NEVER	0 1 2 3 4 5 6 7 8 9 10
Do you have difficulty staying asleep?	ALWAYS	NEVER	
Do you have restlessness of legs or arms at night or in the evening causing disruption of sleep?	ALWAYS	NEVER	
• Do you fidget in bed?	I- ALWAYS	NEVER	
Do you suffer from distressing dreams at night?	ALWAYS	NEVER	0 1 2 3 4 5 6 7 8 9 10
 Do you suffer from distressing hallucination at night (seeing or hearing things that you are told do not exist)? 	ALWAYS	NEVER	
Do you get up at night to pass urine?	ALWAYS	NEVER	
Do you have incontinence of urine because you are unable to move due to "off" symptoms?	ALWAYS	NEVER	
O.Do you experience numbness or tingling of your arms or legs which wake you from sleep at night?	ALWAYS	NEVER	
1. Do you have painful muscle cramps in your arms or legs whilst sleeping at night?	ALWAYS	NEVER	0 1 2 3 4 5 6 7 8 9 10
2.Do you wake early in the morning with painful posturing of arms or legs?	ALWAYS	NEVER	0 1 2 3 4 5 6 7 8 9 10
3.On waking do you experience tremor?	ALWAYS	NEVER	0 1 2 3 4 5 6 7 8 9 10
4.Do you feel tired and sleepy after waking in the morning?	ALWAYS	NEVER	0 1 2 3 4 5 6 7 8 9 10
5. Have you unexpectedly fallen asleep during the day?	FREQUENTLY	NEVER

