5 PLANNED ANALYSES

5.1 Changes from planned analyses in the Protocol

There are no changes from planned Analyses in the Protocol.

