7.7.1 Analysis of Continuous Pharmacodynamics Data

The following continuous PD parameters and their change from baseline will be summarized by period (run-in [baseline], dosing periods (diary) or treatment period (questionnaire data), and washout) for each appropriate population, using descriptive statistics as specified in Section 7.1 (General Statistical Procedures).

Stool Diary PD parameters:

- CSBM days per week
- CSBM episodes per week (Stage 2 only)
- SBM days per week
- SBM episodes per week (Stage 2 only)
- Average ease of passage
- Average stool consistency
- Days using rescue meds per week
- Number of rescue meds use per week

Sleep Diary PD parameters:

- Total sleep time (hours) per day
- Delay (minutes) in sleep onset per night
- Total awake time (hours) per night
- Number of wakes per night
- Number of arm or leg thrashing days per week

Questionnaire PD parameters:

- Total score from NMSQ
- Total score from BDI-II
- Total score from MMSE
- Total score from UM-PDHQ
- Total scores from PFS-16
- Total score and 3 subdomain scores from PAC-SYM
- Total Score and 4 subdomain scores from PAC-QoL
- Total Score from RBDQ
- Total score and Part I to III scores from UPDRS

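### The SAP reduces the PDSS, a protocol exploratory endpoint and the only dedicated sleep questionnaire with one-week recall, to a listing without giving a reason or declaring the change

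*SAP*

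**What the plan says.** Protocol 2.2 lists the PDSS among the other exploratory endpoints of Stage 2. Protocol 10.5 plans exploratory analyses that extend to the "overall NMS scale and all other questionnaires and neurocognitive tests", with comparisons within patients over time and between arms. Sleep is named in the exploratory objective of SAP 3.2.2, and Protocol 4.2 says the population is enriched for sleep delay, sleep fragmentation and REM behaviour disorder.

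SAP 4.4.3.10 then states, together with Trail Making A and B: "Parkinson's disease Sleep Scale (PDSS) will not be used for analyses but will be listed only". SAP 5.1 states: "There are no changes from planned Analyses in the Protocol". SAP section 9 declares two dropped analyses, both of the success endpoint. The list of reasons for the SAP amendment in its Introduction does not mention the PDSS.

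SAP 7.7.1 summarises change from baseline by period for, among others, the NMSQ total and "Total Score from RBDQ". The three instruments refer to different times:

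- PDSS (Protocol Appendix 19): experience "during the past one week".
- NMSQ (Appendix 9): "Have you experienced any of the following in the last month".
- RBDQ (Appendix 18): no recall window. Item 6 opens "I have or had the following phenomena during my dreams", and item 10 asks in the same present-or-past form about nervous-system disease, with Parkinsonism as an example.

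All three share one row of the Stage 2 schedule, both under the July 2017 protocol (SAP Table 3) and under the February 2018 amendment (SAP Table 4).

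**The concern.** Two things look wrong. First, a protocol-planned exploratory result disappears without a declaration, so a reader who relies on SAP 5.1 would believe the questionnaire analyses are intact. Second, the scale removed is the dedicated sleep questionnaire whose recall period best matches the Stage 2 periods. The two questionnaires kept beside it mix time on and off drug, or do not refer to a dated period at all. At stake is a readable questionnaire result on sleep in a population selected partly for sleep problems. A flat RBDQ or NMSQ table could also be taken to show no effect in a given period, which those forms are poorly placed to show.

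**Working it through.** **1. Declaration.** Set side by side, Protocol 10.5 includes all questionnaires and neurocognitive tests, SAP 4.4.3.10 removes the PDSS and Trail Making A and B from analysis, SAP 5.1 says nothing changed, and section 9 lists two other changes. SAP 5.1 is therefore inaccurate on the PDSS, on Trail Making, and against the SAP's own section 9. The February 2018 protocol is not among the documents. SAP 2.1 says that, apart from the Stage 2 dose range and the removal of randomization, nothing else changed from July 2017.

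**2. Length of Stage 2 dosing.** Inputs are 3 days per dose level and 2 to 4 further fixed-dose days (Protocol 3.1, Period 3.2), and 75 to 175 mg in 25 mg steps, which is 5 levels (SAP 2.1).

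- Maximum for Period 3.2: 5 × 3 + (2 to 4) = 17 to 19 days. This reproduces the duration stated for Period 3.2. The design table in Protocol section 3 gives at most 17 days, and the two need reconciling.
- Minimum: 3 + 2 = 5 days.
- With the 6 randomized days on ENT-01: 5 + 6 = 11 to 19 + 6 = 25 days. The upper figure matches the Stage 2 maximum in Protocol section 11.
- February 2018 range, 100 to 250 mg, 7 levels, assuming the same day rule: 7 × 3 + (2 to 4) = 23 to 25 days at most.

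No Stage 2 course fills a month.

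**3. Share of the recall window that lies in the state being measured** (July 2017 schedule, month taken as 30 days):

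| Assessment | Days in state | NMSQ | PDSS |
|---|---|---|---|
| Visit 3, shortest course | 5 on drug | 5/30 = 17% | 5/7 = 71% |
| Visit 3, longest course | 19 on drug | 19/30 = 63% | 100% |
| Visit 4, ENT-01 arm, shortest | 11 on drug | 11/30 = 37% | 100% |
| Visit 4, ENT-01 arm, longest | 25 on drug | 25/30 = 83% | 100% |
| Washout Day 14 | 14 off drug | 14/30 = 47% | 100% |

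Taking a month as 28 to 31 days changes little: the 5-day share is 16% to 18% and the 25-day share 81% to 89%. At Visit 3, 30 − 19 = 11 to 30 − 5 = 25 of the recalled NMSQ days precede the first dose. At the shortest course the PDSS week also reaches 7 − 5 = 2 days before dosing.

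**4. RBDQ.** Items 1 to 5 give 5 points, 6.1 to 6.4 give 4, and 7 to 10 give 4: 5 + 4 + 4 = 13, the maximum in SAP 4.4.3.8. The present-or-past wording governs 6.1 to 6.4 and item 10, so 5/13 = 38% of points cannot go from yes to no if answered as worded. The other 8/13 = 62% can move but are undated. SAP 4.4.3.8 scores an unanswered item as 0, so a skipped item would look like improvement.

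**The case against.** The strongest reply is that sleep and non-motor change are already well covered. SAP 4.4.2 and 7.7.1 analyse five nightly-diary measures by period: sleep time, delay to onset, time awake, number of wakes, and thrashing days. SAP 7.7.2 adds disappearance of thrashing. A nightly diary fits a short period better than any questionnaire. UPDRS Part I, with one-week recall and items on sleep problems and daytime sleepiness, is summarised too, though only as a part score. Questionnaires are exploratory (SAP 4.4.3), their summaries are descriptive (SAP 7.7.1), and SAP section 1 says the SAP supersedes the protocol's statistics. All of this stands, and it limits the impact.

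A reader might infer that the SAP cannot detect a sleep effect, or that the RBDQ is useless for change. The documents do not support either reading. The diary is analysed, 8 of 13 RBDQ points can move, and item 10, constant in this population, cancels from change. A month's recall dilutes change without hiding it. Nor do the documents say when or why the PDSS was set aside, so no motive can be inferred.

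The timing argument is also confined to Stage 2. Stage 1 dosing runs 22 to 57 days, so a one-month recall there falls mostly or wholly within the dosing period.

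What the reply does not answer is the missing declaration. The SAP may change the protocol's plan, but it should not then state that nothing changed.

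**Conclusion.** The point holds as a modest one. One protocol-named exploratory scale, and Trail Making with it, is withdrawn from analysis without a reason and against the statement in SAP 5.1. In Stage 2 that scale matches the periods better than the NMSQ (17% to 83% of a 30-day window on drug at Visits 3 and 4 in the ENT-01 arm) or the undated RBDQ (38% of points unable to fall from yes). No primary endpoint, hypothesis test or safety output is affected.

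The figures assume a 30-day month, the three-day and 2-to-4-day dosing rules as written, and RBDQ answers that follow the wording. The table in the working applies to the July 2017 schedule. For the amended schedule, only the conclusion that dosing stays under a month carries over, on the assumption that the day rule is unchanged.

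**What to change.** Before database lock, since SAP section 7 treats anything designed later as post hoc:

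1. Add PDSS total score and change from baseline by period to SAP 7.7.1, and take the PDSS out of the listed-only sentence in 4.4.3.10. Add a scoring rule to 4.4.3 that covers missing items and direction. Appendix 19 shows 15 items on 0-to-10 lines running from worst to best, so a simple sum would run to 15 × 10 = 150, with higher meaning better sleep.
2. Correct SAP 5.1 and section 9 so that they declare every departure from Protocol 10.5, including Trail Making A and B if it stays listed only.
3. Keep the RBDQ and NMSQ change summaries, which the protocol also planned. Footnote the NMSQ's one-month recall and the RBDQ's undated present-or-past items, so that a flat result is not read as absence of effect in that period.

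The cost is one more exploratory table, from data already collected, and a scoring rule. The Stage 1 schedule table must also be reconciled: it omits the PDSS, although the Stage 1 text in Protocol 3.1 (Periods 1, 2.1 and 2.2) names it.
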